7.8. Summary of Reasons for Efficacy Non-Evaluability/Exclusion from Efficacy Analyses

Reasons for excluding individual patients from the FAS will be summarized and listed.

7.9. Exploratory Analyses

7.9.1. Joint Rank Test

Joint rank analyses using the combined assessment of function and survival (CAFS) ([Berry 2013](#)) will be conducted to account for survival time in the analyses of change in the percent predicted SVC and ALSFRS-R total score at Week 12, individually.

Each patient will be compared with all others in the analysis population in a pairwise manner on their survival status and the functional measurements, ie, changes from baseline in the percent predicted SVC or ALSFRS-R total score. A score of +1 or -1 will be assigned if one has better or worse outcome than the other, respectively. The following rule will be used:

- Patients who died are ranked worse than those who survived.
- Among patients who died, patients who died first are ranked worse.
- For patients who discontinued treatment early but were alive, comparison is based on the last time-point measurements that are both available for the patients in pairs. A patient is ranked worse if the patient discontinued treatment early and did not have functional measurement collected before the discontinuation.
- Among patients who completed, patients with greater decline from baseline in the functional measurement are ranked worse.
- If it is not possible to assign either patient as having the better outcome, then the score assigned to the pair is 0.

For each patient, the assigned scores from the pairwise comparisons with all others will first be summed, and all patients in the analysis population will be ranked according to their summated scores to create a rank score from 1 for the lowest summated score to N (total number of patients in the analysis population) for the highest summated score. If ties occur, each of the tied summated scores will be assigned the average of the ranks the tied summated scores would have if there were no ties.

The rank scores will be analyzed using the generalized Gehan-Wilcoxon test. In addition, the rank scores will be analyzed using an ANCOVA model that adjusts for baseline variables (baseline functional measurement, time from symptom onset, site of disease onset and riluzole or edaravone use). The rank scores between the reldesemtiv and placebo groups will be compared, and the least square mean difference as well as the p-value will be presented.

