5.8. Early Termination Visit

If a patient decides to terminate early from the study, they should be seen in the clinic as soon as possible following discontinuation of study drug. The following procedures will be performed:

1. 12-lead ECG
2. Vital signs including heart rate, blood pressure, and respiratory rate measured after the patient has been resting for at least 3 minutes
3. Weight
4. Abbreviated physical examination
5. Neurological examination
6. Clinical laboratory evaluations, including CBC and WBC with differential, serum chemistries, cystatin C and UA

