5.15. Removal of Patients from Study Participation

Patients will be informed that they are free to discontinue study drug or withdraw from the study at any time and for any reason. The Investigator may discontinue study drug or withdraw a patient from the study if, in the Investigator's opinion, it is not in the best interest of the patient to continue the study. Patients may discontinue study drug or withdraw from the study due to the following:

- a. A change in compliance with inclusion/exclusion criteria that is clinically relevant and/or affects patient safety, and/or study assessments/objectives, etc.
- b. Occurrence of intolerable AEs
- c. Changes in vital signs, ECGs, or clinical laboratory results that, in the opinion of the Investigator, pose a significant health risk
- d. Intake of non-permitted concomitant medication that might affect patient safety or study assessments/objectives, etc.

- e. eGFR calculated using the CKD-EPI cystatin equation (Inker, Schmid et al. 2012) shows a >25% decline compared to baseline (defined as Day 1 or Screening if Day 1 value is not available) as long as the decline is not related to dehydration or a superimposed reversible process such as infection or nausea.
- f. Changes in liver function tests (LFTs) as outlined in [Appendix C](#)
- g. Receiving any form of stem cell therapy for ALS either as part of a clinical trial or outside of a clinical trial
- h. Having a diaphragmatic pacing system implanted either as part of a clinical trial or outside of a clinical trial
- i. Initiating edaravone after screening.
- j. Initiating riluzole after screening.
- k. Initiating gene therapy for ALS either as part of a clinical trial or outside of a clinical trial after screening.

Patients should be strongly encouraged to perform the early termination visit as soon as possible following last dose of study drug taken, and the Follow-Up Visit should be performed 28 days after last dose taken of study medication. In addition, they should be encouraged to return for all remaining study visits and assessments (with the exception of 12-lead ECG, clinical laboratory and PK sampling) for the duration of the study following study drug discontinuation. These remaining study visits should be performed according to the original study visit windows.

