Patients who decide to start or stop edaravone or riluzole after screening and before randomization, will no longer be eligible to be randomized and should not be followed subsequently. If a patient decides to start edaravone or riluzole after randomization, they will be terminated from taking study medication once that is known by the site. They should return to the clinic for their early drug termination visit as soon as possible following last dose of study drug taken and return 28 days after last dose taken for the Follow-Up Visit. They will not be followed thereafter.

For patients who terminate early from the study and do not want to return to the clinic for the visits as described in the above paragraph, phone call visits should be performed to collect the information if the patient is willing (see [Section 5.8](#)).

Notification of discontinuation will immediately be made to the Sponsor's Medical Monitor. In case of withdrawal of study participation, efforts will be made to perform Early Termination ([Section 5.8](#)) and Follow-Up visit assessments ([Section 5.7](#)). The date the patient is withdrawn from the study and the reason for discontinuation will be recorded on the patient's eCRF. All patients who prematurely discontinue from the study for AEs will be followed for up to 30 days, until the AE resolves, or until the unresolved AE is judged by the Investigator to have stabilized.

The primary reason for a patient prematurely withdrawing from the study should be selected from the following categories and documented in the source documents:

- a. Patient Death
- b. Adverse Event: One or more clinical or laboratory events which, in the medical judgment of the Investigator, are grounds for discontinuation even if the event does not appear to be related to study medication. The patient may withdraw because of an AE even if the Investigator does not feel that the event is grounds for discontinuation.
- c. Protocol Violation: The patient's findings or conduct failed to meet the protocol entry criteria or failed to adhere to the protocol requirements

- d. Patient Withdrawal of Consent: Patient desires to withdraw from further participation in the study and reason for doing so.
- e. Administrative/Other: Any cause of premature termination from the study other than the above, such as illness of investigator, loss of study drug, or termination of study by the Sponsor.

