5.4. Analysis Sets

5.4.1. Full Analysis Set

The Full Analysis Set (FAS) will consist of all randomized patients who received any amount of study drug and have a baseline and at least one post baseline efficacy assessment during the double-blind treatment.

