7.5. Analysis of the Primary Efficacy Endpoints

7.5.1. Primary Efficacy Analysis

The primary efficacy endpoint (change from baseline to Visit Week 12 in percent predicted SVC) will be analyzed for the FAS based on the percent predicted SVCs collected in clinic and were confirmed evaluable by the central read of an independent pulmonologist. A MMRM with the contrast (-5, -1, 3, 3) will be used for the analysis to reflect the assumed relationship for the placebo, 300 mg/day, 600 mg/day and 900 mg/day dose groups. The response variable will be the change from baseline to each post baseline visit up to Week 12. The model will include the following covariates:

- Treatment (reldesemtiv 300 mg/day, 600 mg/day and 900 mg/day, and placebo)
- Baseline (baseline value of the response variable)
- Pooled site (Center)
- Visit (scheduled, a categorical variable)
- Riluzole and edaravone use status at baseline
- Treatment-by-visit interaction
- Baseline-by-visit interaction

An unstructured variance-covariance structure will be used to model the within-subject errors. If a model fails to converge, other covariance matrix structures (eg, compound symmetry) may be used instead of the unstructured covariance matrix. Least square means and the corresponding standard errors, 95% CIs and p-values will be presented.

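### The exploratory joint-rank test penalises a living patient for stopping drug before any functional measurement, even when function was measured later, and its FAS restriction can leave out early deaths

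*SAP*

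**What the plan says.** SAP 7.9.1 compares every pair of patients on survival and then on change in percent predicted SVC or ALSFRS-R.

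- Deaths come last: "Patients who died are ranked worse than those who survived".
- For living patients who stopped treatment early, "comparison is based on the last time-point measurements that are both available for the patients in pairs". No limit to on-drug values is stated.
- The same bullet adds: "A patient is ranked worse if the patient discontinued treatment early and did not have functional measurement collected before the discontinuation".
- A pair that cannot be ordered scores 0.

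Function can be measured after drug stops. Protocol 5.15 says of patients who stop that "they should be encouraged to return for all remaining study visits and assessments", apart from ECG, laboratory and PK sampling. Patients who start edaravone or riluzole after randomisation are the exception. After an early termination visit and the 28-day Follow-Up Visit, "They will not be followed thereafter". Protocol 5.8 times the Early Termination Visit after the stop: "they should be seen in the clinic as soon as possible following discontinuation of study drug". That visit includes SVC and ALSFRS-R, and ALSFRS-R may be taken by telephone if the patient will not attend.

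SAP 5.5.4 and 5.5.5 assign early-discontinuation measurements to visit windows and let them become analysed records. SAP 7.5.1 sets no on-drug limit for the primary model: "The response variable will be the change from baseline to each post baseline visit up to Week 12".

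Table 2 in SAP 5.4.4 assigns the FAS to all of Section 7. FAS members must "have a baseline and at least one post baseline efficacy assessment during the double-blind treatment".

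**The concern.** The rule overrides an observed value. Suppose a patient stops drug on Day 8, attends the Early Termination Visit on Day 10 and returns through Week 12 with stable SVC and ALSFRS-R. The Day 10 value falls in the Week 2 analysis window (Days 2 to 21, SAP Appendix B), and the Week 12 value exists. If nothing was measured before Day 8, 7.9.1 still ranks this patient below a survivor who lost many points. The primary model would use the same data, provided the patient is in the FAS.

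What is at stake is the direction of an exploratory result. If one arm has more very early stopping, the rule turns that into apparent functional loss in that arm. It could hide a benefit or suggest a harm.

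The second problem concerns deaths. The test is there to bring survival into the comparison, yet a treated patient who dies before any post-baseline efficacy assessment is not in the FAS and is not counted.

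**Working it through.** **1. The plan's own figures.** Inputs from Protocol 8.1.2: contrast (-5, -1, 3, 3), advantages 0, 2.75, 5.5 and 5.5 points, SD 14, about 400 completers (100 per arm), two-sided alpha 0.05.
- Contrast value: -1 × 2.75 + 3 × 5.5 + 3 × 5.5 = 30.25. Sum of squared coefficients: 25 + 1 + 9 + 9 = 44.
- Standard error: 14 × √(44/100) = 9.29. Power: Φ(30.25/9.29 − 1.96) = 90.3%, which matches the stated 90%.
- 400/0.9 = 444.4, which rounds up to the stated 445.

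The documents give no power figure for the joint-rank test.

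**2. How many patients the rule could reach.** The first post-baseline clinic visit is Week 2 (Day 15). The documents do not say how many patients stop before it. If the planned 10% dropout had a constant hazard (assumption), the share by Week 2 would be 1 − 0.9^(2/12) = 1.74%. That is about 8 of 445, or 2 per arm, before the FAS requirement removes any.

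The FAS phrase matters here.
- If it means the 12-week period, patients with only off-drug values are in the FAS and the rule applies to them.
- If it means on drug, most are excluded. The rule then reaches those with some other on-drug efficacy value. One example is a patient with a home SVC or voice recording (weekly after Day 1) before stopping, but no ALSFRS-R until after the stop.

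**3. Direction and size of the bias.** Let p0 and p1 be the shares of placebo and active patients caught, and θ the chance that an uncaught active patient beats an uncaught placebo patient. With no deaths, and ties counted as one half:
- Win probability under the rule = 0.5·p0·p1 + p0(1 − p1) + θ(1 − p0)(1 − p1).
- Under the null θ = 0.5, and this reduces to 0.5 − (p1 − p0)/2. Equal shares give no bias.
- For a 5.5-point effect θ = Φ(5.5/(14√2)) = 0.609.
- If off-drug values are used and carry no drug effect, win probability = θ(1 − p1) + 0.5·p1.

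**4. Illustration.** Assumptions not in the documents: the shares caught, normal changes with SD 14, 112 per arm, all early stoppers followed to Week 12, no deaths. Rejection rates are from a simulated two-arm rank test; repeat runs move them by about one percentage point.

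| Caught, placebo v active | Null win probability | Null rejection | Win probability, 5.5 points: rule / off-drug values | Power: rule / off-drug values |
|---|---|---|---|---|
| 1% v 3% | 0.49 | 5.5% | 0.595 / 0.606 | 70% / 79% |
| 1% v 5% | 0.48 | 8% | 0.583 / 0.604 | 58% / 78% |
| 1% v 8% | 0.465 | 14% | 0.565 / 0.601 | 39% / 74% |

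**5. Check under other assumptions.** Here there are 111 per arm, 1% deaths per arm and 1.74% of placebo caught.
- Null rejection under the rule is 4.7% with no imbalance, 6.1% with 2 points more on drug, 8.1% with 4 more and 23% with 10 more. The excess is almost all against the drug.
- With off-drug values it stays between 4.8% and 5.1%.
- Power, rule v off-drug values, is 77% v 78%, 67% v 77%, 54% v 74% and 20% v 69%.
- If the three doses are pooled (111 v 334), null rejection under the rule is 5.6% and 9.7% for the 2-point and 4-point imbalances.

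**The case against.** **The documents do not point to an imbalance.** Protocol 1.3 says dizziness, headache and nausea appeared dose-related. It also places the increase at 2250 mg and above and reports no Phase 1 discontinuations for adverse events. The highest dose here is 450 mg twice daily, and Protocol 3.3 expects the doses to be well tolerated. A reader might infer that early stopping on drug is to be expected; the text does not support that. The 5% and 8% scenarios put half to four-fifths of the planned 10% dropout before the first visit. This objection stands, so the figures are conditional.

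**Full follow-up is assumed.** Protocol 5.15 only encourages return, and patients who start riluzole or edaravone are not followed. This also stands: the gain from using off-drug values depends on how many exist.

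**The FAS may already remove the affected patients.** On the on-drug reading it removes most, but not those with another on-drug efficacy value. Because the phrase can be read either way, it does not settle the matter.

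**Stronger readings that fail.**
- A reader might say such a patient ranks worst of all. Deaths rank lower, so this is true only among survivors.
- A reader might say off-drug values are discarded for every early stopper. The preceding sentence sets no such limit for patients with a value before the stop.
- A reader might say the test measures tolerability. The rule reaches mainly patients who stop before about Day 15, and stopping need not reflect intolerance.
- A reader might say every death before the Week 2 visit is lost. A home assessment can qualify a patient for the FAS, so only deaths before any post-baseline efficacy assessment are lost.

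**The analysis is exploratory.** It is outside the testing sequence in SAP 7.4, and the primary endpoint has its own missing-not-at-random sensitivity analysis in SAP 7.5.2. This limits the importance of the point but does not make the rule right.

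**Conclusion.** The point holds in a limited form. As worded, 7.9.1 ranks a living patient below other survivors for stopping drug before any functional measurement, whatever was measured afterwards. That conflicts with the protocol's off-drug follow-up and with the SAP's own windowing rules. The bias needs unequal very early stopping; with equal stopping, power falls by only a point or so. A 4-point imbalance would move the null win probability to 0.48 and cost about 20 points of power for a 5.5-point effect, assuming full follow-up and no residual drug effect. At the planned dropout with constant hazard, only about 2 patients per arm would be exposed to the rule.

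The exclusion of some early deaths follows from the FAS definition and needs no assumption about imbalance. Its size cannot be derived, because the documents give no early death rate. The primary and secondary tests are untouched. The SAP wording should be corrected, but nothing confirmatory depends on it.

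**What to change.** In SAP 7.9.1:

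1. Compare survivors on change from baseline at the last visit up to Week 12 at which both have a value, whether on or off study drug.
2. Apply any missing-data rule only to patients with no post-baseline functional value at all. The existing score-0 bullet can cover these pairs. A score of 0 is neutral towards a patient lost through rapid progression, so the sponsor may keep a worse rank as a sensitivity analysis.
3. Run the test on all randomised patients who received any study drug (the Safety Analysis Set definition), so that early deaths count.

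SAP 5.4.1 should also say whether its closing phrase means on drug or the 12-week period.

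The cost is SAP wording, minor programming and a few more tied pairs. No extra data are needed. A patient without a baseline functional value could be ranked on survival but would drop out of the baseline-adjusted ANCOVA in 7.9.1, which the text should note.

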7.9.2. Time-To-Event Analysis for Muscle Strength

Time-to-event analysis will be performed for muscles that had a measurable muscle strength at baseline. The muscle strength measured by HHD will be analyzed using proportional hazard Cox regression model. The event is defined as muscle strength as measured by HHD equals 0 from any muscle in the evaluated muscle groups. For patients who had the event, the date of muscle strength reached 0 will be used as the event date. For patients who did not have the event, data will be censored at their last date of study visit. Kaplan-Meier method will be used to summarize the time to event, and median, 95% CIs of the median, Q1, Q3, and range will be provided.

7.9.3. Evaluation of SVC Measured at Home Using SVC Measured in Clinic as the Standard

In addition to performing SVC assessments in clinic, GoSpiro home spirometer was given to patients for collecting their SVC data weekly from home. However, the usage of the spirometer varies among patients due to different reasons (eg, patients forgot to take the assessments or had technical difficulties, etc.). Hence it is of interest to evaluate consistency of the SVCs measured at home vs. the SVCs measured in clinic. Also, there may be potential learning effect due to more frequent use of the spirometer that may resulting in higher SVC assessed later on. The analyses to be used for the evaluations are described in the following sections.

7.9.3.1. Correlation Between at Home and in Clinic Assessments of SVC

The test-retest reliability of SVC measured at home will be assessed using the measures in clinic as the standard for each patient. Each measure at home will be paired with a measure in the clinic within a seven-day of window. Correlation between at home and in clinic SVC assessments overall and by visit will be evaluated using Pearson correlation coefficient and paired t-test.

7.9.3.2. Change from Baseline to Week 12 in Percent Predicted SVC Assessed at Home and in Clinic

The SVC assessed at home and in clinic will be combined for a supportive analysis of change from baseline to Week 12 in percent predicted SVC. A MMRM will be used for the analysis. The response variable will be the change from baseline to each post baseline visit up to Week 12. The model will include the following covariates:

- Treatment (reldesemtiv 300 mg/day, 600 mg/day and 900 mg/day, and placebo)
- Location of SVC collection (at home or in clinic)
- Baseline (baseline value of the response variable)
- Pooled site
- Time (time from the first dose, a continuous variable)
- Riluzole and edaravone use status at baseline
- Baseline-by-time interaction
- Treatment-by-time interaction

An unstructured variance-covariance structure will be used to model the within-subject errors. If a model fails to converge, other covariance matrix structures (eg, compound symmetry) may be used instead of the unstructured covariance matrix. Least square means and the corresponding standard errors, 95% CIs and p-values will be presented.

7.9.3.3. Time to Event Analysis of Percent Predicted SVC Decline to Less Than 50%

To evaluate consistency of the SVCs measured at home vs. that measured in clinic, percent predicted SVC collected during clinic visits and at home will be analyzed using a proportional hazard Cox regression model. The event is defined as percent predicted SVC decline to less than 50% during the 12 weeks of the study. For patients who had the event, the first date of SVC less than 50% will be used as the event date. For patients who did not have the event, data will be censored at their date of study visit or Week 12 visit, whichever is earlier. Kaplan-Meier method will be used to summarize the time to event for percent predicted SVC measured in clinic and at home, separately. The median of the time to event, 95% CIs of the median, Q1, Q3, and range will be provided.

7.9.3.4. Comparing Percent Predicted SVC Between Patients Who Used a Home Spirometer for SVC Assessments and Those who Never Used

To evaluate the potential learning effect of using a spirometer and its impact on the percent predicted SVC measured in clinic, the use of the spirometer will be added as a covariate in the MMRM for a supportive analysis of change from baseline to Week 12 in percent predicted SVC and be evaluated for if it's a significant factor in predicting the outcome. The rates of decline (ie, slope) in percent predicted SVC assessed in clinic will also be compared between patients who performed SVC assessments using the home spirometer and those who did not use. In addition, since SVC will be assessed 3 times in each clinic visit, the variation among the 3 measurements collected at each visit will be compared between patients who used the home spirometer for SVC assessments and those who did not use.

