2.2.4. Exploratory Efficacy Endpoints

Endpoints assessed as a change from baseline include:

- Change from baseline to Visit Week 12 in the percent predicted SVC measured at home
- Change from baseline to Visit Week 12 in the components of voice analysis
- Change from baseline to Visit Week 12 in the components of handwriting analysis
- Percent change in the strength of the muscle groups from baseline to Visit Week 12 that contribute to the Mega score at Visit Week 12
- Change from baseline to Visit Week 12 in the ALSAQ-5

Endpoints assessed as a change in slope include:

- Slope of change from baseline to Visit Week 12 in the percent predicted SVC
- Slope of change from baseline to Visit Week 12 in the ALSFRS-R
- Slope of change from baseline to Visit Week 12 in percent predicted SVC measured at home
- Slope of change from baseline to Visit Week 12 in the components of voice analysis

- Slope of change from baseline to Visit Week 12 in the components of handwriting analysis
- Slope of change from baseline to Visit Week 12 in the ALSAQ-5

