5.5.8.1. Percent Predicted Slow Vital Capacity

SVC is used to evaluate pulmonary status. It is the maximum volume of air that can be exhaled slowly after slow maximum inhalation. The percent predicted SVC presents the test result as a percent of the predicted values for patients based on sex, age, height, and race. It is calculated as: $\text{Percent Predicted SVC} = (\text{Trial SVC} / \text{Predicted SVC}) \times 100 (\%)$

The predicted SVC is calculated using the Quanjer GLI-2012 Regression Equation ([Quanjer 2012](#)) that factor the characteristics of sex, age, height and race into the prediction.

For male,

$$\begin{aligned} \text{Predicted SVC} = & \exp [-11.2281 + 2.4135 \times \ln(\text{Height})(\text{cm}) + 0.0865 \times \ln(\text{Age})(\text{yrs}) \\ & - 0.1684 \times \text{AfrAm} - 0.0405 \times \text{NEAsia} - 0.1177 \times \text{SEAsia} \end{aligned}$$

$$- 0.0825 \times \text{Other} + \text{Mspline}]$$

For female,

$$\begin{aligned} \text{Predicted SVC} = & \exp [-10.403 + 2.2633 \times \ln(\text{Height})(\text{cm}) + 0.0234 \times \ln(\text{Age})(\text{yrs}) \\ & - 0.1555 \times \text{AfrAm} - 0.0262 \times \text{NEAsia} - 0.1516 \times \text{SEAsia} \\ & - 0.0833 \times \text{Other} + \text{Mspline}] \end{aligned}$$

where

$\ln()$ = natural log transformation

AfrAm = 1 if a patient is African American, otherwise = 0

NEAsia = 1 if a patient is from North East Asia, otherwise = 0

SEAsia = 1 if a patient is from South East Asia, otherwise = 0

Other = 1 if a patient belongs to other ethnic group or has mixed ethnicity, otherwise = 0

Mspline is determined by age and sex as shown in [Appendix D](#).

For each clinical visit, a patient's SVC was evaluated in triplicate. The highest result among the evaluable measurements confirmed by the central read of an independent pulmonologist will be used for analysis (ie, measurements not confirmed as evaluable by the central read will be excluded from analysis). For SVCs measured at home, the highest result among the evaluable measurements collected during a day will be used for analysis, where 'evaluable' is defined as a measurement of SVC is not smaller than 0.5 times and not greater than 1.5 times of the highest evaluable SVC measured in clinic during the same week.

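### SAP 7.9.3.1 compares home with clinic SVC by Pearson correlation and a paired t-test only, which leaves the scatter of individual differences and level-dependent bias unreported

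*SAP*

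**What the plan says.** SAP 7.9.3.1 falls under the exploratory analyses of Section 7.9. It states its purpose as follows: "The test-retest reliability of SVC measured at home will be assessed using the measures in clinic as the standard for each patient". On pairing it says: "Each measure at home will be paired with a measure in the clinic within a seven-day of window". The relation between the two sources, overall and by visit, "will be evaluated using Pearson correlation coefficient and paired t-test". A home reading enters only if it passes the rule in SAP 5.5.8.1, that is, if it is "not smaller than 0.5 times and not greater than 1.5 times of the highest evaluable SVC measured in clinic" in the same week.

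The section plans no SD of the paired differences, no limits of agreement, no intraclass or concordance correlation and no acceptable difference.

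Three other parts of SAP 7.9.3 touch on home readings:

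- 7.9.3.2 pools home and clinic values in one repeated-measures model with location as a main effect.
- 7.9.3.3 looks at time to percent predicted SVC below 50%, separately by source, with an aim that begins "To evaluate consistency of the SVCs measured at home vs. that measured in clinic".
- 7.9.3.4 compares patients who used the home spirometer with those who did not.

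Home SVC is itself an exploratory endpoint (SAP 2.2.4: "Change from baseline to Visit Week 12 in the percent predicted SVC measured at home", with a matching slope endpoint). The primary analysis in SAP 7.5.1 uses only clinic readings confirmed as evaluable by the central read.

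**The concern.** Reliability against a standard is a question about the size of the differences between paired readings. Pearson r does not measure that. Adding a constant to every home reading, or multiplying every one by the same factor, leaves r unchanged, and a more varied set of patients raises r with no gain in accuracy. The paired t-test addresses only the mean difference.

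Two features can therefore pass unseen: the scatter of individual differences around their mean, and a bias that is positive at low SVC and negative at high SVC, so that it averages out. What is at stake is the reading of the home SVC endpoints and of the pooled analysis in SAP 7.9.3.2. For both, one wants to know how closely a home value tracks the clinic value.

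**Working it through.** **1. The plan's own figure.** The documents give no figure for agreement. The only calculation that uses SVC variability is the power statement in SAP 3.3.1: SD 14, contrast (-5, -1, 3, 3), effects 2.75, 5.5 and 5.5, and about 400 completers, so 100 per arm.

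- Contrast value: -1×2.75 + 3×5.5 + 3×5.5 = 30.25.
- SE: 14×√(44/100) = 9.287, where 44 = 25 + 1 + 9 + 9.
- Power: Φ(30.25/9.287 − 1.96) = 90.3%, against the stated 90%. It reproduces.

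That SD of 14 is for change from baseline. It is neither the between-patient SD of percent predicted SVC nor the SD of home-clinic differences, so what follows rests on assumed values.

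**2. Limits of agreement implied by r.** With equal SDs for the two sources and zero mean bias, the variance of the difference is 2×SD²×(1 − r). The 95% limits are ±1.96×SD×√(2(1 − r)), in points of percent predicted:

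| Assumed between-patient SD | r = 0.85 | r = 0.90 | r = 0.95 |
|---|---|---|---|
| 14 | ±15.0 | ±12.3 | ±8.7 |
| 17 | ±18.3 | ±14.9 | ±10.5 |
| 20 | ±21.5 | ±17.5 | ±12.4 |

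The range is about ±9 to ±21 points.

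**3. The typical miss.** Limits of ±15 mean an SD of differences of 15/1.96 = 7.65. The median absolute difference is then 0.6745×7.65 = 5.2 points. About 5% of differences exceed 15 points and about 19% exceed 10.

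**4. Can both planned statistics look good together?** A simulation (2,000 runs; 100, 200 or 400 pairs; clinic values with mean 85 and none below 50; all error placed on the home reading; zero bias; SD of differences 7.65) gave mean r of 0.87, 0.90 and 0.92 for assumed SDs of 14, 17 and 20. The t-test was non-significant in about 95% of runs at every size, as it should be when the mean bias is zero. A correlation near 0.9, a non-significant t-test and limits of ±15 therefore fit together.

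**5. Level-dependent bias.** Take a mean clinic SVC of 80 and suppose home = 40 + 0.5×clinic. Then r = 1 and the mean difference is 40 + 0.5×80 − 80 = 0. Yet a patient at 60 in clinic reads 70 at home, and a clinic decline of 5.5 points shows as 2.75. The case is artificial, but both statistics would report perfect agreement.

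**6. What the t-test does detect.** With an SD of differences of 7.65 and independent pairs, the smallest significant mean offset is 1.96×7.65/√n: 1.5, 1.1 and 0.75 points at 100, 200 and 400 pairs.

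**7. The evaluability rule.** Clinic values of 60, 80 and 100 admit home readings of 30–90, 40–120 and 50–150. In the simulation the rule removed under 0.01% of readings.

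**8. Repeated pairs.** In the overall analysis a patient can contribute a pair at several visits. If differences within a patient correlate at ρ and there are m pairs each, the SE of the mean difference grows by √(1 + (m − 1)ρ). With m = 4 and an assumed ρ of 0.5 this is √2.5 = 1.58; with ρ = 0 it is 1. The documents give no value for ρ.

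**The case against.** The strongest reply is that little depends on this analysis. It is exploratory, the primary analysis does not use home values, and SAP 7.9.3 says only that consistency is of interest. That stands, and it limits the weight of the point.

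The paired t-test also deserves credit. It detects a constant offset, and a purely proportional error shifts the mean too: 5% at a level of 80 is 4 points. The gap is scatter, and bias that cancels on average. SAP 5.1 also lists the SD, minimum and maximum for continuous variables; applied to the paired differences, these would give the limits almost directly. SAP 7.9.3.1 does not say that they will be.

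Sections 7.9.3.2 to 7.9.3.4 do not fill the gap. A location main effect estimates a mean offset, time to below 50% by source describes a threshold event, and users against non-users is a different comparison.

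A reader might infer more than the documents support:

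- **That home readings are usually wrong by about 15 points.** Such a figure is an outer 95% limit under assumed inputs, and it covers clinic error as well. If the two sources shared error equally, ±15 would mean 15/√2 = ±10.6 for the home reading alone.
- **That the limits should be set against the 5.5-point target effect.** One is a range for individual differences, the other a difference between group means. The ratio says nothing about whether home SVC is adequate for group comparisons.
- **That the 0.5–1.5 rule inflates r.** Step 7 shows almost no effect under ordinary error. It could matter only by removing gross failures, and their number is unknown.
- **That pooling pairs makes the t-test flag trivial bias.** If errors are independent from pair to pair, pooling is valid and a small significant bias merely reflects a large sample. Clustering matters only if patients carry a persistent bias, which the documents do not quantify.
- **That home spirometry is meant to replace clinic SVC.** Neither document proposes this.

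**Conclusion.** The point holds as a low-cost improvement to an exploratory analysis. The two planned statistics describe linear association and mean offset, whereas the stated aim is reliability against a standard. The size of what they leave out cannot be taken from the documents: about ±9 to ±21 points follows from an assumed SD of 14 to 20, an assumed r of 0.85 to 0.95, equal SDs and zero mean bias. The actual limits could lie outside that range. The conclusion about method does not depend on these values, because r and a mean test cannot supply the missing quantity whatever they are. No confirmatory result is touched.

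**What to change.** Add to SAP 7.9.3.1, by visit and overall:

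- the mean home-minus-clinic difference and its 95% limits of agreement, each with a confidence interval;
- in the overall analysis, a patient random effect, because patients contribute repeated pairs;
- an intraclass or concordance correlation;
- a Bland-Altman plot, which would also show bias that varies with SVC level.

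Keep Pearson r as a descriptive figure. Report how many home readings the 0.5–1.5 rule in SAP 5.5.8.1 removes.

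The cost is a few lines of SAP text, one table and one plot, from data already being collected. The primary analysis and the sample size do not change.
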